10.2. DEFINITION OF STUDY POPULATIONS

Dose escalation part

- Population assessable for DLT assessment :
 - Patients assessable for the DLT assessment must fulfill all the following criteria:
 - Completed the DLT assessment period
 - Received concomitantly at least seven consecutive days of Olaparib and radiotherapy treatment (any dose) at least once.
 - Unless they develop a DLT, the following patients will not be included in the population assessable for DLT :
 - Patients who did not receive radiotherapy
 - Patients who did not receive nor Olaparib;
 - Patients who did not complete the full DLT evaluation period and goes off-treatment for reasons other than toxicity;

These patients will be replaced to reach the sample size requirement for dose escalation study.

- Safety population: patients who received radiotherapy or olaparib, at least once, irrespective of the dose. .

Expansion cohort

- Eligible population: All patients included without major violation of eligibility criteria.
- Population eligible and assessable for the primary endpoint : patients who fulfill all criteria below:
 - Eligible patients
 - Received concomitantly at least seven consecutive days of Olaparib and radiotherapy treatment (any dose) at least once.
 - at least one disease measurement recorded not less than eight weeks after treatment onset.

The following patients will also be included in the population evaluable for efficacy; they will be considered as failures for the primary endpoint (i.e. progressive disease at 6 months) and not be replaced in the efficacy analysis:

- Eligible patients withdrawn due to drug-related toxicity without any tumor assessments after the start of study treatment.
- Eligible patients withdrawn due to significant clinical deterioration of unknown reason, hypersensitivity reactions, or unrelated AEs without any tumor assessments after the start of study treatment.
- ***Replacement of patients: patients who do not comply with the definition of the population "eligible and assessable for the primary endpoint" will be replaced to reach the sample size requirement for expansion cohort.***
- Safety population: patients who receive at least one administration of Olaparib, or radiotherapy treatment at least once.

10.3. STATISTICAL ANALYSIS

A statistical Analysis Plan (SAP) will be produced by the statistician of the study and validated by the steering committee. A preliminary version will be produced prior to the first inclusion. The SAP will be updated when necessary (Substantial modification of the protocol, IDMC recommendations, etc) and systematically validated by the steering committee.

Dose escalation part

- Dose-toxicity modeling
 - At the end of the trial, the posterior distribution of the dose-toxicity parameter α and DLT at each dose, will be estimated using the power dose-toxicity model and normal prior distribution on α used to conduct the trial.
 - 95% posterior intervals for the toxicity probabilities will be reported.
- Patient characteristics at baseline will be provided
 - Compliance with eligibility criteria,
 - Epidemiological characteristics,
 - Clinical and laboratory characteristics,
 - Treatment characteristics.
- Toxicities observed at each dose level will be recorded in terms of event type, severity, dates of beginning and end, reversibility and evolution. Data will be gathered in tables summarizing toxicities.
- Efficacy analysis: efficacy endpoints will be reported in terms of counts and proportions for each dose levels. Subgroup analyses will be conducted for metastatic and non-metastatic patients.
- All analyses will be descriptive; no p-values will be calculated.
- Data analyses will be provided by dose groups and for all study patients, combined wherever appropriate.
- For continuous variables, summary statistics will include number of patients, median, minimum, and maximum, and additional percentiles if appropriate.
- Categorical endpoints will be summarized using number of patients, frequency, percentages.
- For survival endpoints, median survival time will be reported.
- Missing data will not be imputed.

Expansion cohort

- Patient characteristics at baseline will be provided
 - Compliance with eligibility criteria,
 - Epidemiological characteristics,
 - Clinical and laboratory characteristics,
 - Treatment characteristics.
- Toxicities will be recorded in terms of event type, severity, dates of beginning and end, reversibility and evolution. Data will be gathered in tables summarizing toxicities and side effects for each dose level and cycle.
- Efficacy analysis: efficacy endpoints will be reported in terms of counts and proportions. Subgroup analyses will be conducted for metastatic and non-metastatic patients.
- All analyses will be descriptive; no p-values will be calculated.
- For continuous variables, summary statistics will include number of patients, median, minimum, and maximum, and additional percentiles if appropriate.
- Categorical endpoints will be summarized using number of patients, frequency, percentages.
- For survival endpoints, median survival time will be reported.
- Missing data will not be imputed.
- Pharmacokinetics
 - PK analyses will be based on all subjects who receive at least one dose of Olaparib, if appropriate. Deviations from this will be documented.
 - PK parameters (AUC, C_{max}, t_{1/2}) of Olaparib will be calculated using noncompartmental methods, and the systemic clearance (CL) will be derived from the plasma concentrations via standard methods.
 - All pharmacokinetic parameters will be presented descriptively including arithmetic means, standard deviations, geometric means, and coefficients of variation, medians and ranges.

- Pharmacodynamics (translational research). Given the small number of subjects, analyses will be descriptive. The distribution of the biomarkers will be reported for subgroups of patients defined by their response to treatment.

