2.2.2. Expansion cohort

- Preliminary signs of anti-tumor activity of Olaparib given with concomitant radiotherapy in terms of 6-month objective response, objective response under treatment, best response under treatment, 1-year progression-free survival (PFS) and 1-year overall survival (OS). Subgroup analyses will be conducted for metastatic and non-metastatic patients.
- Toxicity profile of Olaparib given with concomitant radiotherapy.
- Pharmacokinetics (PK) of Olaparib.
- Functional assessment before and after treatment using the Muskuloskeletal Tumor Society functional form (MSTS; Enneking et al. Clin Orthop 1993).
- Pharmacodynamics (translational research): Prognostic markers of anti-tumor activity of Olaparib given with concomitant radiotherapy will be investigated.

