 - Stopping rule: inclusions will stop in the dose escalation trial after 24 eligible and assessable patients enrolled.
- For the dose escalation part, a DLT validation committee will be consulted before the first escalation to a new dose level (see section 12.1.2).
- Conclusions of the steering committee for the MTD definition will be submitted to an independent committee (IDMC) before opening the expansion cohort.

3.5.EXPANSION COHORT

- Once the MTD and the RP2D have been defined based on the dose escalation study, the expansion cohort will be opened. All patients will be treated at the RP2D of Olaparib (as defined in the escalation trial) given in association with concomitant radiotherapy at a dose that depends on tumor status:
 - Resectable tumor or potentially resectable tumor after study treatment: up to 50 Gy
 - Unresectable tumor: up to 59.4 Gy.
- Following the expansion cohort, the **RP2D for Olaparib** may be refined by the steering committee based on the MTD and RP2D (as defined at the end of the dose escalation trial), as well as additional safety data including safety data from the expansion cohort, PK and PD data. Data from all patients (escalation + expansion) will be used to refine the RP2D.

3.6.PATIENT'S REPLACEMENT

See section 10.2

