4. SELECTION OF PATIENTS

4.1. INCLUSION CRITERIA

1. Histology: patients with soft-tissue sarcoma histologically confirmed by central review (Pr [name] team), except if the diagnosis was already confirmed by the RRePS Network,
2. Upper/Lower limb or trunk wall soft-tissue sarcoma,
3. Age ≥ 18 years,
4. Locally advanced or locally recurrent primitive tumor, outside any previously irradiated field. Patients presenting operable locally advanced or locally recurrent tumor can be included. Patients with metastases can be included in the protocol,
5. Eastern Cooperative Oncology Group (ECOG), performance status ≤ 2 ,
6. Life expectancy ≥ 6 months,
7. At least one lesion, not previously irradiated, that can be accurately measured at baseline as ≥ 10 mm in the longest diameter (except lymph nodes which must have short axis ≥ 15 mm) with magnetic resonance imaging (MRI) and which is suitable for accurate repeated measurements,
8. Adequate hematological, renal, metabolic and hepatic function:
 - Haemoglobin ≥ 9 g/dL and no blood transfusions in the 14 days prior to study entry
 - Absolute neutrophil count (ANC) $\geq 1.5 \times 10^9/L$
 - Platelets $\geq 100 \times 10^9/L$
 - Total bilirubin $\leq 1.5 \times$ upper limit of normality (ULN),
 - Alanine aminotransferase (ALAT) or aspartate aminotransferase (ASAT) $\leq 2.5 \times$ ULN,
 - Serum creatinine $\leq 150 \mu\text{mol/L}$ or creatinine clearance $\geq 50 \text{ mL/min}$ (according to local institution) in case of serum creatinine $> 150 \mu\text{mol/L}$,
 - TP, INR $\leq 1.5 \times$ ULN
9. Women of childbearing potential must have a negative serum pregnancy test within 28 days of study treatment, confirmed prior to treatment on day 1. Female patients of child bearing potential and their partners, who are sexually active, must agree to the use of two highly effective forms of contraception in combination throughout the period of taking study treatment and for at least 1 month after last dose of study drug. Males patients, who are sexually active, and their partners of child bearing potential must agree to the use of two highly effective forms of contraception in combination throughout the period of taking study treatment and for at least 3 month after last dose of study drug. Acceptable birth control methods are described in appendix 6. Subjects of non-childbearing potential are those who have:
 - Amenorrheic for 1 year or more following cessation of exogenous hormonal treatments,

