7.2.4. Dose prescription, specification and reporting in the PTV

Dose prescription, specification and reporting will be done according to ICRU report 83 recommandations.

During DOSE ESCALATION PHASE:

The prescribed dose at the median of the PTV (for IMRT treatments) or at the ICRU point (for non-IMRT treatments) will be 59.4Gy in 33 fractions of 1.8Gy, with 5 fractions per week.

During EXPANSION PHASE: Total radiotherapy dose will be adapted with patient condition (operable patient/inoperable patient):

- Up to 50 Gy for resectable disease or potentially resectable disease after study treatment (in 25 fractions of 2 Gy, with 5 fractions per week)
- Up to 59.4 Gy for unresectable disease (in 33 fractions of 1.8Gy, with 5 fractions per week).

95% of the PTV will have to receive at least 95% of the prescribed dose. Dose homogeneity inside the PTV will have to be comprised between 95% and 107% of the prescribed dose. The maximal dose should not exceed 107% of the prescribed dose.

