	
 
The steering committee will meet before proceeding to each dose escalation.
 
Conclusions of the steering committee for the definition of the MTD and the RP2D will be submitted to an independent committee (IDMC) before opening the expansion cohort.
 
 
EXPANSION COHORT
 
Once the MTD and the RP2D has been defined based on the dose escalation study, the expansion cohort will be opened. All patients will be treated at the RP2D of Olaparib (as defined in the escalation trial) given in association with concomitant radiotherapy with the same schedule as in the phase I trial. Following the expansion cohort, the RP2D for Olaparib may be refined by the steering committee based on the MTD and RP2D (as defined at the end of the dose escalation trial), as well as additional safety data including safety data from the expansion cohort, PK and PD data. Data from all patients (escalation + expansion) will be used to refine the RP2D.

Translational research	
For consented patients, a tumor tissue biopsy sample is required to be collected at inclusion, at Day 8 of Cycle 1 before the start of the radiotherapy and one month after the end of the radiotherapy (ie. week 12). Patients must provide additional consent for these optional tumor tissue biopsy samples.
 
 
Analysis of the tumor tissue samples may include, but not be limited to:
 
DNA extraction and sequencing in order to identify: 
 
If the patient has a mutation in BRCA1, BRCA2, or another gene in the HR repair pathway
 
If a patient has a BRCA reversion or other mutation(s) that may be associated with response or resistance to olaparib plus radiotherapy
 
 
 
DNA extraction and sequencing of single nucleotide polymorphisms (SNPs) to identify genomic scars and to determine whether genomic scarring can be used as a predictor of olaparib + radiotherapy response
 
Immunohistochemistry analysis to assess NHEJ pathway integrity, cleaved Caspase-3 and γ-H2AX staining pre- and on treatment (week 4)
 
Gene expression profiling on extracted RNA to potentially identify a signature associated with response to olaparib + radiotherapy
 

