Inclusion criteria	
 
Histology: patients with soft-tissue sarcoma histologically confirmed by central review (Pr [name] team), except if the diagnosis was already confirmed by the RRePS Network,
 
Upper/Lower limb or trunk wall soft-tissue sarcoma,
 
Age ≥ 18 years,
 
Locally advanced or locally recurrent inoperable tumor, outside any previously irradiated field (inoperable status must be assessed by staff including a surgeon specialized in sarcoma),
 
Eastern Cooperative Oncology Group (ECOG) performance status ≤ 2,
 
Life expectancy ≥ 6 months,
 
At least one lesion, not previously irradiated, that can be accurately measured at baseline as ≥ 10 mm in the longest diameter (except lymph nodes which must have short axis ≥ 15 mm) with magnetic resonance imaging (MRI) and which is suitable for accurate repeated measurements,
 
Adequate hematological, renal, metabolic and hepatic function:
 

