	
HRCT scan or any psychiatric disorder that prohibits obtaining informed consent,
 
6. Patients with uncontrolled seizures,
 
7. Men or women of childbearing potential who are not using an effective method of contraception as previously describes; women who are pregnant or breast feeding,
 
8. No prior or concurrent malignant disease diagnosed or treated in the last 2 years, except for adequately treated in situ carcinoma of the cervix, basal or squamous skin cell carcinoma, or in situ transitional bladder cell carcinoma,
 
9. Patients receiving any systemic chemotherapy, radiotherapy (except for palliative reasons), within 2 weeks from the last dose prior to study treatment (or a longer period depending on the defined characteristics of the agents used),
 
10. Concomitant use of known CYP3A4 inhibitors such as ketokonazole, itraconazole, ritonavir, indinavir, saquinavir, telithromycin, clarithromycin and nelfinavir,
 
11. Resting ECG with QTc > 470msec on 2 or more time points within a 24 hour period or family history of long QT syndrome,
 
12. Blood transfusions within 14 days prior to study start,
 
13. Patients with myelodysplastic syndrome/acute myeloid leukaemia,
 
14. Major surgery within 14 days of starting study treatment and patients must have recovered from any effects of any major surgery,
 
15. Participation to a study involving a medical or therapeutic intervention in the last 30 days,
 
16. Patient unable to follow and comply with the study procedures because of any geographical, familial, social or psychological reasons,
 
17. Previous enrollment in the present study,
 
18. Patients with a known hypersensitivity to olaparib or any of the excipients of the product.
																
Route of administration	
Olaparib will be administered per os bi-daily, as appropriate assigned dose level, during 7.5 weeks (D1 to D52). Olaparib should be started one week before the start of radiotherapy and will be continued until the last day of radiotherapy. Beyond this period, Olaparib could be continued at the investigator’s discretion and after sponsor authorization, until progression.
 
Radiotherapy consists of fractionated focal irradiation at a dose of 1.8 Grays (Gy) per fraction given once daily five days per week (Monday through Friday) over a period of 6.5 weeks, for a total dose of 59.4 Gy. Radiotherapy starts at D8.
																

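### Expansion toxicity should be shown by prescribed radiotherapy regimen: the planned tables pool the 50 Gy and 59.4 Gy courses, while every escalation patient is prescribed 59.4 Gy

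*Protocol*

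**What the plan says.** **Radiotherapy.** Protocol 7.2.4 prescribes 59.4 Gy in 33 fractions of 1.8 Gy to all escalation patients. For expansion it prescribes "Up to 50 Gy for resectable disease or potentially resectable disease after study treatment", in 25 fractions of 2 Gy, and up to 59.4 Gy in 33 fractions of 1.8 Gy for unresectable disease. Protocol 3.5 gives the same split, with one olaparib dose (the RP2D) for the whole cohort. Protocol 4.1 allows both kinds of patient: "Patients presenting operable locally advanced or locally recurrent tumor can be included".

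**Use of the toxicity data.** Protocol 2.2.2 lists as an expansion objective: "Toxicity profile of Olaparib given with concomitant radiotherapy". Protocol 3.5 says that the steering committee may refine the RP2D after expansion, and adds: "Data from all patients (escalation + expansion) will be used to refine the RP2D".

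**Tabulation.** Protocol 10.3 (expansion) says: "Data will be gathered in tables summarizing toxicities and side effects for each dose level and cycle". SAP 3.1.1 carries the same sentence for both study parts. SAP 4.2.10 lists adverse event tables by term and by grade. The one planned subgroup, metastatic status, sits in the efficacy bullet of Protocol 10.3.

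**Text that still implies one regimen.** The expansion paragraph of the protocol synopsis, and the same paragraph in SAP 1.1, describe treatment as "given in association with concomitant radiotherapy with the same schedule as in the phase I trial". The route-of-administration entry in SAP 1.1 gives only the longer course, "over a period of 6.5 weeks, for a total dose of 59.4 Gy. Radiotherapy starts at D8", without distinguishing the study parts. The expansion entry under treatment schedule in SAP 1.1 omits the adaptation to resectability. The SAP inclusion criterion is also older: "Locally advanced or locally recurrent inoperable tumor, outside any previously irradiated field".

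**The concern.** The expansion cohort fixes olaparib and lets radiotherapy vary. The toxicity tables are laid out by olaparib dose, which hardly varies, and not by the radiotherapy course, which does. Following the plan therefore gives one toxicity figure for a mixture of two courses.

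That figure would be read beside escalation data from patients who were all prescribed 59.4 Gy. If the two courses carry different toxicity, the comparison reflects how many resectable patients happened to enrol as well as how olaparib was tolerated. The reader of a planned table could not tell which. At stake is the clarity of a stated secondary objective, and of one input to the committee's review of the RP2D.

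**Working it through.** **1. The two courses.** Inputs from Protocol 7.2.4:
- 25 × 2.0 Gy = 50 Gy, as stated.
- 33 × 1.8 Gy = 59.4 Gy, as stated.
- Ceiling in the shorter course: 1 − 50/59.4 = 0.158, about 16% lower. Dose per fraction is higher (2.0 against 1.8 Gy).

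**2. Duration.** Radiotherapy starts on D8, five fractions a week. Assume a Monday start and no interruption. The day of fraction n is 8 + 7 × floor((n − 1)/5) + ((n − 1) mod 5).
- n = 33: 8 + 42 + 2 = D52, which reproduces the protocol's own end date.
- n = 25: 8 + 28 + 4 = D40.

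The courses thus differ in total dose, fraction size and length.

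**3. Can any planned table separate them?**

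| Planned output | Splits toxicity by | Separates the courses? |
|---|---|---|
| Protocol 10.3 (expansion), SAP 3.1.1 | Olaparib dose level and cycle | No: all expansion patients start at the RP2D, and lower levels arise only through dose reduction (Protocol 7.1.6.2) |
| SAP 4.2.10 | Term, grade | No |
| SAP 4.2.6, Tables 6.1 and 6.2 | Delivered Gy and fractions by dose level, not crossed with toxicity | No |
| SAP 4.2.9, Table 9.2 | Radiotherapy dose at onset of an in-field DLT, cut at 30 Gy | No: dose at onset is not the prescribed course |

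Dose level means olaparib level throughout (Protocol 3.4.2).

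**4. Effect of pooling.** Let f be the share of expansion patients on 50 Gy, and r50 and r59 the toxicity rates under the 50 Gy and 59.4 Gy courses. The pooled rate is f·r50 + (1 − f)·r59, so

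pooled − r59 = −f × (r59 − r50).

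The documents give neither f nor the rates, so f is assumed. N = 15 is the planned recruitment (Protocol 10.1).

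| On 50 Gy | f | Gap per 10-point difference |
|---|---|---|
| 5 of 15 | 0.333 | 3.3 points |
| 7 of 15 | 0.467 | 4.7 points |
| 8 of 15 | 0.533 | 5.3 points |
| 10 of 15 | 0.667 | 6.7 points |

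If r50 = r59, the gap is 0 for any mix.

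Illustration with assumed rates: r59 = 33% and r50 = 20%.
- 5 on 50 Gy: (5 × 0.20 + 10 × 0.33)/15 = 28.7%.
- 8 on 50 Gy: (8 × 0.20 + 7 × 0.33)/15 = 26.1%.
- 10 on 50 Gy: (10 × 0.20 + 5 × 0.33)/15 = 24.3%.

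**5. Precision.** Exact (Clopper-Pearson) 95% intervals:
- 3/15 pooled: 4.3% to 48.1%.
- 2/7: 3.7% to 71.0%; 1/8: 0.3% to 52.7%.
- 0/5: 0 to 52.2%; 0/10: 0 to 30.8%.

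One event in 15 is 6.7 points, the same as the largest gap in step 4. A split can display the data by regimen; it cannot establish a difference.

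**The case against.** The case against giving this much weight is strong. All analyses are descriptive and no rule turns on expansion toxicity. The steering committee includes the coordinating investigator and the trial biostatistician and is not confined to pooled tables. SAP Datalisting 2.3 gives dose and fractions per patient. The RP2D only may be refined, on several inputs including PK and PD. The gaps in step 4 rest on assumed case mixes and are small against the intervals in step 5. The synopsis also makes combining data conditional on its being appropriate. All of that stands, and it limits the size of the point. It does not answer it: the listings allow only reconstruction by hand, the adverse event listing (SAP 4.1.5) is produced only if required, and no planned table shows the result.

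A split would not restore full comparability either. Regimen follows resectability by design. Protocol 4.1 does not confine operable patients to expansion, so the escalation patients on 59.4 Gy may include operable ones, whereas the 59.4 Gy expansion stratum is unresectable only. Escalation may supply very few patients at the RP2D (minimum 2 per level, Protocol 10.1).

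Three stronger readings are tempting.

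- *Pooling will make olaparib look safer than it is.* The documents do not support a direction. The shorter course has a lower ceiling but larger fractions, and some of its patients go on to surgery, where wound complications are an expected effect of radiotherapy (Protocol 11.9). The complication figure in Protocol 1.1 concerns doses above 65 Gy.
- *The two groups are observed for different lengths of time.* Six weeks after the last fraction is D82 (40 + 42) against D94 (52 + 42). But Protocol 7.2.5 fixes examinations through D92 with no distinction by regimen, and the assessment schedule collects adverse events throughout the study. Continued olaparib extends reporting, and operated patients have extra visits and 12 months of complication reporting. The contrast is not a reliable bias.
- *The SAP intends a single 59.4 Gy course in expansion.* Its synopsis lags behind the protocol generally, and some of its 59.4 Gy text sits correctly under dose-escalation headings. Protocol 10.3 already commits to updating the SAP. Bringing it up to date would still not add the split, because Protocol 10.3 lacks it too.

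**Conclusion.** The point holds as a gap in reporting. Two prescribed regimens enter one cohort, no planned toxicity table separates them, and the escalation data used alongside come from one regimen. If toxicity differs by regimen, the pooled expansion figure is a case-mix average and is not like-for-like with escalation.

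The size is modest: 3.3 to 6.7 points per 10-point difference under assumed mixes of 5 to 10 of 15 on 50 Gy, and nothing if the rates are equal or only one regimen enrols. The conclusion about the tables rests on the documents alone; the size rests on those assumptions. The documents do not show that toxicity differs, in which direction, or that any dose decision would change. The change is still worth making because it is cheap and makes the safety comparison readable.

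**What to change.** **In Protocol 10.3 (expansion) and SAP 3.1.1 and 4.2.10:** report expansion toxicity by prescribed radiotherapy regimen beside the overall figure, as descriptive n/N with exact 95% intervals and no test.

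**Classification:** take the regimen from a prescribed-regimen (resectability) field, not from delivered dose per fraction. The safety population in Protocol 10.2 includes patients who received olaparib only, and anyone who stops in D1 to D7 has no fractions from which to infer a regimen.

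**At the RP2D review:** show escalation patients treated at the RP2D beside the 59.4 Gy expansion patients, with the 50 Gy patients in a separate column.

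**Caveats to print with the table:** regimen is confounded with resectability; operable patients are not excluded from escalation; strata of about 5 to 10, and possibly very few escalation patients at the RP2D, cannot establish a difference.

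**Wording:** correct the same-schedule sentence in the expansion paragraphs of the protocol synopsis and SAP 1.1. State both courses in the route-of-administration entry and the expansion treatment-schedule entry of SAP 1.1. The SAP changes belong in the update already foreseen.

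**Cost:** a few sentences, extra table columns and one named variable. Radiotherapy dose and fractions are already listed per patient. The SAP names no prescribed-regimen field; whether the case report form holds one cannot be seen from the documents. The drawback is wide intervals in small strata, so the split should stand beside the pooled figure and not replace it. The plan already accepts a descriptive subgroup of similar size, efficacy by metastatic status.
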